### 5.3. Adjustments for Covariates

The study is stratified by country, baseline HbA1c ( $\leq 8.5\%$ ,  $> 8.5\%$  [ $\leq 69$ ,  $> 69$  mmol/mol]), and baseline SGLT2 inhibitor use (Yes or No). Where necessary to be included as a stratification factor, countries with fewer than 10 randomized patients will be pooled into one category (pooled country). For HbA1c related analyses, country/pooled country and baseline SGLT2 inhibitor use will be used as stratification factors and baseline HbA1c as a covariate. For other efficacy analyses, country/pooled country, baseline HbA1c ( $\leq 8.5\%$ ,  $> 8.5\%$  [ $\leq 69$ ,  $> 69$  mmol/mol]), and baseline SGLT2 inhibitor use (Yes or No) will be used as stratification factors and respective baseline value as a covariate.

Stratification factors will be derived based on the data collected from the clinical database.

### 5.4. Handling of Dropouts or Missing Data

For the primary and key secondary efficacy endpoint analyses subject to type 1 error rate control, data for patients with missing values at the 52-week visit will be imputed based on the method describe in Section 5.12.1.3. Unless specified otherwise, imputation of missing data will be limited to primary and key secondary efficacy endpoint analysis. Missing other secondary or exploratory efficacy parameter values and missing safety laboratory values will not be explicitly imputed.

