3.1. Study Rationale

Type 2 diabetes mellitus (T2DM) is a metabolic condition characterized by impaired glycemic control caused by increased insulin resistance and successive beta-cell failure and consequently inadequate insulin secretion. Type 2 diabetes mellitus is frequently associated with comorbidities such as increased weight or obesity, hypertension, and increased blood lipoprotein concentrations. Patients with T2DM have a higher risk for cardiovascular diseases (CVDs) particularly arteriosclerotic diseases in the heart and in the central nervous system. In case of prevalent arteriosclerotic diseases and/or chronic kidney diseases (CKD) of T2DM patients, the likelihood of a subsequent, life-threatening major cardiovascular (CV) event is very high, up to 2% to 4%/year (Haffner et al. 1998). To prevent these, complex medical therapy is warranted beyond the necessary changes in lifestyle and diet. Among others, patients have to achieve a tight glycemic control by combination of various antihyperglycemic medications (American Diabetes Association 2017). The diabetes therapy usually starts with lifestyle and diet changes followed by 1 or more oral medications. When oral antihyperglycemic therapies are insufficient to reach the therapy goal of target glycemia, injectable therapies are added to them. Insulins, especially basal insulins, like glargine, are basic injectable treatments after failure of the oral therapy. Adequately titrated glargine therapy, in combination with oral treatment, frequently achieves the target glycemic level. Glargine therapy, however, is frequently associated with weight increase and eventual hypoglycemia. LY3298176 is a 39-amino acid synthetic peptide with agonist activity at both the GIP (glucose-dependent insulinotropic polypeptide) and GLP-1 (glucagon-like peptide-1) receptors. Its structure is based on the GIP sequence and includes a C20 fatty di-acid moiety. It is administered once weekly (QW) by subcutaneous (SC) administration. The aim of the present study is to compare the glycemic effect of glargine and LY3298176 in patients with T2DM and elevated risk for CVD. In addition, the number of major cardiovascular outcome events (MACE-4) to be collected in the study with high CV risk patients, will largely contribute to establishing the cardiovascular safety of LY3298176 prior to submission for license, as requested by the regulatory agencies. The study could also compare the effect of these drugs on weight loss and their safety profile.

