#### 3.2. Key Secondary Objectives Subject to Strong Type 1 Error Rate Control

Together with the primary objectives, the following secondary objectives are subjected to strong control of type 1 error rate (see Section 5.12.3).

- To demonstrate that QW tirzepatide 5 mg is noninferior to insulin glargine for change from baseline in HbA1c at 52 weeks.
- To demonstrate that QW tirzepatide 5 mg, 10 mg, and/or 15 mg is superior to insulin glargine for change from baseline in weight at 52 weeks.
- To demonstrate that QW tirzepatide 5 mg, 10 mg, and/or 15 mg is superior to insulin glargine for change from baseline in HbA1c at 52 weeks.
- To demonstrate that QW tirzepatide 5 mg, 10 mg, and/or 15 mg is superior to insulin glargine for the proportion of patients with HbA1c target values of <7.0% (53 mmol/mol) at 52 weeks.

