## 5.12. Efficacy Analysis

For the FDA and potentially for other regulatory agencies, all efficacy assessments will be guided by the “treatment-regimen” estimand conducted using FAS. Assessment of the primary and secondary efficacy objectives subject to type 1 error rate control (key secondary) will be conducted with multiple imputation of missing data (see Section 5.12.1.3) at 52 weeks.

Assessment of other efficacy objectives will be conducted without imputation of missing data. For publications and other purposes, the assessment of efficacy objectives will be guided by the “efficacy” estimand using EAS set without imputation of missing data. A listing of patients randomized but not included in efficacy analyses (ie, not treated, discontinued treatment due to inadvertent enrollment) will be provided.

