#### **5.12.1.3. Methods for Multiple Imputations**

For efficacy analysis relative to “treatment-regimen” estimand, missing HbA1c data at the 52-week visit will be imputed based on “retrieved dropouts,” defined as patients who had their HbA1c value measured at the 52-week visit in the same treatment arm who prematurely discontinued study drug. If the imputed value of HbA1c change from baseline is  $< -6.0\%$  or  $> 6.0\%$ , that value will be set to  $-6.0\%$  or  $6.0\%$ , respectively, to avoid unrealistic imputed values.

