### **5.12.2.3. Proportion of Patients Achieving HbA1c $<7\%$ at the 52 week Visit**

The analysis relative to the “efficacy” estimand for the endpoint at 52 weeks will be conducted using EAS with missing values imputed from an MMRM model and then dichotomized. The MMRM model includes country/pooled country, SGLT2 inhibitor use at baseline, treatment, visit, and treatment-by-visit interaction as fixed effects, and baseline HbA1c as a covariate. After dichotomizing continuous HbA1c, the data is analyzed using a logistic regression model with treatment, country/pooled country, SGLT2 inhibitor use at baseline, and baseline HbA1c as a covariate. In addition, analysis will be conducted utilizing data using EAS from baseline through the 52-week visit with the aid of a longitudinal logistic regression with repeated measurements with country/pooled country, SGLT2 inhibitor use at baseline, treatment, visit, treatment-by-visit interaction as fixed effects, and baseline HbA1c as a covariate. In the case that longitudinal logistic model does not converge due to small number of events, logistic regression will be utilized to analyze proportion of patients achieving HbA1c $<7\%$  at nominal visits.

Analysis relative to “treatment-regimen” estimand will be conducted utilizing HbA1c data in FAS at baseline and at the 52-week visit with the aid of a logistic regression with multiple imputation of missing HbA1c data at the 52-week visit (see Section 5.12.1.3 for details). Model terms will include treatment, country/pooled country, SGLT2 inhibitor use at baseline as fixed effects, and baseline HbA1c as a covariate and statistical inference over multiple imputations will be guided by Rubin (1987).

[figure not shown]

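### In the treatment-regimen analysis of HbA1c <7% at Week 52, patients who die first are imputed from same-arm drug discontinuers measured at Week 52, so some deaths count as achieving the target

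*SAP*

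**What the plan says.** SAP 3.2 lists, among the objectives under strong type 1 error control, superiority of each tirzepatide dose to "insulin glargine for the proportion of patients with HbA1c target values of <7.0% (53 mmol/mol) at 52 weeks".

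For these endpoints SAP 5.4 gives one general rule: "data for patients with missing values at the 52-week visit will be imputed based on the method describe in Section 5.12.1.3". SAP 5.12.1.3 then sets the method for the treatment-regimen estimand. The retrieved dropouts who serve as donors are "defined as patients who had their HbA1c value measured at the 52-week visit in the same treatment arm who prematurely discontinued study drug". SAP 5.12.2.3 carries this into the responder endpoint through "a logistic regression with multiple imputation of missing HbA1c data at the 52-week visit".

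Death has no rule of its own in the efficacy analyses:

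- The full analysis set (SAP 5.1) and the list of patients left out of efficacy analyses (SAP 5.12) remove only untreated patients and those who stopped treatment because they were enrolled inadvertently.
- The treatment-regimen estimand (SAP 5.2) addresses adherence and rescue therapy only.
- SAP 5.2 mentions death as one way in which study participation ends, and assigns no endpoint value to it.
- Protocol 10.3.3.1 and 10.3.3.2 are equally silent on death.

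**The concern.** A treatment-policy strategy uses the value that is observed whatever happens to treatment. After death there is no Week-52 HbA1c, so the value is not one that better follow-up could have recovered. Imputing it matters most for a binary target, because the imputed number is turned into success or failure. Every donor was alive at Week 52. Protocol 8.1.1 allows patients who stop study drug to receive another glucose-lowering treatment, so some donors can be below 7%. A share of the patients who died will then be reported as having reached the target at 52 weeks.

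The population is selected for increased cardiovascular risk (Protocol 6.1, criterion 4), so some deaths before Week 52 should be expected. What is at stake is the meaning of a confirmatory responder rate and, to a smaller degree, the comparison between arms.

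**Working it through.** **Inputs from the documents.** Protocol 10.1 gives 313 patients per tirzepatide dose and 939 on glargine, 1878 in all. Its stated 90% power for superiority in mean HbA1c reproduces: the standard error is 1.3 × √(1/313 + 1/939) = 0.0848, 0.30/0.0848 = 3.54, and 3.54 − 2.24 = 1.29, which gives power 0.902 at two-sided 0.025. This confirms the arm sizes. It says nothing about deaths, and no planning figure exists for the responder endpoint.

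**Inputs that are assumptions.** Neither mortality to Week 52 (d) nor the share of donors below 7% (q) is in the documents. Take d = 1-3% and q = 30-50%.

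**Step 1: what the rules do with a death.** A treated patient dies at, say, Week 30. The patient stays in the full analysis set, has no Week-52 HbA1c, and so falls under 5.4. Under 5.12.1.3 the value comes from living same-arm donors. Under 5.12.2.3 it enters the <7% logistic regression. On average a fraction q of such patients are successes.

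**Step 2: size within an arm.** Deaths = n × d. Deaths counted as responders = n × d × q. Rise in the arm's proportion = d × q.

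| | Low (d 1%, q 30%) | High (d 3%, q 50%) |
|---|---|---|
| Deaths, dose arm (313) | 3.1 | 9.4 |
| Deaths, glargine (939) | 9.4 | 28.2 |
| Counted as responders, dose arm | 0.9 | 4.7 |
| Counted as responders, glargine | 2.8 | 14.1 |
| Rise in proportion, either arm | 0.3 points | 1.5 points |

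The chance that at least one death somewhere in the trial is a responder in a given imputed data set is 1 − (1 − q)^deaths. With 19 deaths (1%) and q = 30% this is 1 − 0.7^19 = 0.999. Even with q = 10% it is 1 − 0.9^19 = 0.86.

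**Step 3: size for the comparison.** The difference moves by d_T × q_T − d_G × q_G, where T is a tirzepatide dose and G is glargine.

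- Equal mortality and equal q: 0.
- Equal mortality at 3%, q of 50% against 30%: 3% × 20% = 0.6 points.
- A wider donor gap, 50% against 20%: 0.3 points at 1% mortality and 0.6 points at 2%.
- Unequal mortality can reverse the sign. With q = 30% in both arms, 1% mortality on the dose and 3% on glargine, the shift is 0.3 − 0.9 = −0.6 points, in favour of glargine.

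Near 50% response, the standard error of the difference is √(0.25/313 + 0.25/939) = 3.3 points, so 0.6 points is under one fifth of it.

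**Step 4: effect on power in an unfavourable case.** Assume 60% against 50% responders among survivors, two-sided 0.05, and q of 50% against 20%. Counting deaths as failures lowers power from 0.882 to 0.862 at 1% mortality and from 0.894 to 0.855 at 2%. With 75% against 50% among survivors, power stays near 1 either way.

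**The case against.** No sentence says that deaths are imputed; this follows from a general rule and the absence of an exception. That is true, but the rule as written does reach them, and nothing elsewhere removes them.

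A stronger objection is consistency. If HbA1c after death does not exist, the same is true in the analyses of mean HbA1c and body weight, which would be left as planned. The logic does reach the means. The difference is practical: for a target endpoint, failure is a natural value for death, whereas for a mean any assigned number would be arbitrary. Counting death as failure is still a choice of strategy, and the documents do not dictate it.

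Reporting is also partly covered. SAP 5.13.1.1 lists deaths by treatment, and SAP 5.7 summarises disposition before Week 52 by arm. This helps a reader, but it does not change the responder rate.

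A reader might infer four stronger points that the documents do not support:

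- **That the controlled test is materially biased.** Both arms shift in the same direction. With equal mortality the net effect is 0 to about 0.6 points, and a large donor gap cannot be presumed because donors in every arm have stopped study drug.
- **That the other responder thresholds in SAP 5.12.4 share the fault.** Missing data are not imputed there (SAP 5.4, 5.12 and 5.12.4).
- **That the documents supply a death rate.** Protocol 3.1 puts the likelihood of a later "life-threatening major cardiovascular (CV) event is very high, up to 2% to 4%/year", and Protocol 10.1 assumes 33 to 40 MACE-4 patients per 1000 patient-years. Both are event rates; MACE-4 includes non-fatal events.
- **That the living-discontinuer route covers both estimands.** For the efficacy estimand the <7% analysis "will be conducted using EAS with missing values imputed from an MMRM model and then dichotomized". Deaths receive a value there too, but by a separate route.

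**Conclusion.** The point holds for the treatment-regimen analysis of HbA1c <7% at Week 52. Followed exactly, the plan counts some patients who died as having achieved the target in a type-1-error-controlled endpoint. Assuming 1-3% mortality and 30-50% of donors below 7%, an arm's proportion is raised by about 0.3-1.5 percentage points. With equal mortality across arms, the difference between arms moves by 0 to about 0.6 points. Both ranges rest on assumptions, since the documents give neither quantity. The defect lies mainly in what the reported responder rate means and is unlikely to decide the test. It is worth correcting because the endpoint is confirmatory and the correction is simple.

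**What to change.** Add one sentence to SAP 5.12.2.3: for the treatment-regimen estimand, patients who die before the Week-52 HbA1c measurement are set to not achieving <7% in every imputed data set, and the number of such deaths is reported by arm. Leave the continuous HbA1c and body weight analyses, the SAP 5.12.4 endpoints and the efficacy-estimand analysis as they are; this change does not touch the MMRM route.

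The cost is one sentence and one line of code. No new data are needed, because dates of death are already collected. The downside is slightly lower responder rates, by the 0.3-1.5 points shown above if the assumptions hold.

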### 5.5. Multicenter Studies

To investigate potential regional influence on efficacy, country/pooled country will be used as a stratification factor in primary and secondary efficacy analysis.

### 5.6. Multiple Comparisons/Multiplicity Adjustments

Type 1 Error rate control strategy for primary and key secondary efficacy objectives is illustrated in Section 5.12.3. As they are intended for different purposes, no multiplicity adjustments will be made for conducting separate analyses relative to “efficacy” and “treatment-regimen” estimands. No multiplicity adjustments will be made for evaluating other secondary and exploratory efficacy objectives and safety assessments.

### 5.7. Patient Disposition

Reasons for screen failure as reported by investigators will be summarized.

A listing of final study disposition and a listing of randomized treatment assignment (planned treatment) for all randomized patients will be provided. Final study disposition and treatment disposition for all randomized patients will be summarized by planned study treatment. Patient study disposition prior to the 52-week visit (when the primary endpoint is ascertained) as well as at or after the 52-week visit will be summarized by planned study treatment.

## 5.8. Patient Characteristics

Listing of patient demographics will be provided. All demographic and baseline clinical characteristics will be summarized by study treatment for the patients in the mITT population. Baseline demographic and clinical characteristics of special interest include: age, gender, race, ethnicity, weight, country of enrollment, HbA1c, fasting serum glucose, duration of type 2 diabetes, baseline antihyperglycemic medication, CV history, estimated glomerular filtration rate (eGFR), urine albumin-to-creatinine ratio (UACR), results of the fundoscopic exam, history of gallbladder disease, and percentage of patients who have renal impairment (defined as baseline eGFR < 60 mL/min/1.73m^2 or baseline UACR > 300 mg/g).

## 5.9. Concomitant Therapy

The prespecified concomitant medications of interest will be summarized by treatment at randomization. Additionally medications of interest initiated after randomization and change to medications of interest used at randomization will be summarized. The concomitant therapies will be mapped using the World Health Organization (WHO) DRUG dictionary in the clinical trial database and will be further classified using Anatomic-Therapeutic-Chemical (ATC) codes for reporting purposes.

The concomitant medications of interest include the following groups of medication:

- Baseline Antihyperglycemic therapy
  - Prior GLP-1 RA use by type
  - Metformin
  - Sulfonylureas, by type
  - SGLT2-inhibitors, by type
- Baseline antihypertensive therapy, by type
- Baseline lipid lowering therapy, by type
- Changes to baseline medication
  - Antihyperglycemic therapy
  - Antihypertensive therapy
  - Lipid lowering therapy
- Rescue therapy
- Initiation of following medications in Study Period II/III:
  - Antidiarrheal medication
  - Antiemetic medication

## 5.10. Treatment Exposure and Compliance

Listing of patients randomized but not receiving study treatment will be provided, if applicable. The listing will include patient identification, randomized treatment arm, and the reason for not receiving study treatment.

Summary of duration of follow-up (defined as time in days from date of randomization to date of safety follow-up) and duration on study treatment (defined as time in days from date of first dose of study treatment to date of last dose of study treatment plus 7 days) will be provided by therapy.

### 5.10.1. Exposure and Compliance to Tirzepatide

Number of patients prematurely discontinuing study treatment prior to the 52-week visit as well as before the end of efficacy follow-up will be provided by study treatment. Reasons for prematurely discontinuing study treatment prior to the 52-week visit as well as before the end of efficacy follow-up will be provided by study treatment. Time-to-event analysis of premature study treatment discontinuation will be conducted.

Proportion of patients with missing dosing information, receiving no tirzepatide dose, receiving 2.5mg, 5mg, 7.5mg, 10mg, 12.5mg or 15mg will be presented by randomized treatment and week from first dose.

Listing and summary of patients continuing on a reduced maintenance dose of tirzepatide compared to the randomized dose may be provided.

The compliance will be defined as taking at least 75% of the scheduled tirzepatide doses. Compliance will be calculated by taking the number of doses administered (regardless the actual dose administered) divided by the total number of doses expected to be administered  $\times 100$ . Treatment compliance will be summarized descriptively over the entire study period by treatment using the mITT population.

### 5.10.2. Exposure and Compliance to Insulin Glargine Treat-to-Target Algorithm

Summary information of total daily dose of insulin glargine will be reported by visit. Information related to compliance to treat-to-target therapy including reasons for non-compliance will be summarized.

Compliance will be defined as taking at least 75% of the scheduled insulin doses. Compliance will be calculated by taking the number of injections expected minus the total number of injections missed (regardless of the actual dose administered) divided by the total number of injections expected to be administered  $\times 100$ . Treatment compliance will be summarized descriptively using the mITT population.

## 5.11. Important Protocol Deviations

Important protocol deviations are identified in Trial Issues Management Plan (TIMP). A listing and a summary of Important protocol deviations by treatment will be provided.

## 5.12. Efficacy Analysis

For the FDA and potentially for other regulatory agencies, all efficacy assessments will be guided by the “treatment-regimen” estimand conducted using FAS. Assessment of the primary and secondary efficacy objectives subject to type 1 error rate control (key secondary) will be conducted with multiple imputation of missing data (see Section 5.12.1.3) at 52 weeks.

Assessment of other efficacy objectives will be conducted without imputation of missing data. For publications and other purposes, the assessment of efficacy objectives will be guided by the “efficacy” estimand using EAS set without imputation of missing data. A listing of patients randomized but not included in efficacy analyses (ie, not treated, discontinued treatment due to inadvertent enrollment) will be provided.

### 5.12.1. Primary Efficacy Analysis

The primary efficacy measure will be change in HbA1c from baseline (post-baseline – baseline) at 52 weeks. Both HbA1c values as well as change from baseline in HbA1c will be summarized by treatment and nominal visit (week). When applicable, HbA1c data from a local lab will be used when central lab data is not available. If scheduled HbA1c data at the primary endpoint visit is not available, unscheduled HbA1c data collected for the primary endpoint visit will be included in analysis.

#### 5.12.1.1. The Analysis Relative to the Efficacy Estimand

The analysis will be conducted utilizing HbA1c data in EAS from baseline through the 52-week visit with the aid of a mixed model for repeated measures (MMRM). Restricted maximum likelihood (REML) will be used to obtain model parameter estimates and Kenward-Roger option will be used to estimate denominator degrees of freedom. The response variable of the MMRM model will be the primary measure and model terms will include treatment, visit, treatment by visit interaction, country/pooled country, and SGLT2 inhibitor use at baseline as fixed effects, and baseline HbA1c as a covariate. An unstructured covariance structure will be used to model the within-patient errors. If this model fails to converge, the following covariance structures will be tested in order:

- Heterogeneous Toeplitz;
- Heterogeneous First Order Autoregressive;
- Heterogeneous Compound Symmetry;
- Toeplitz;
- First Order Autoregressive;
- Compound Symmetry.

The first covariance structure that converges will be used. Resulting Least Squares Mean (LSM) estimate of mean change from baseline in HbA1c will be plotted by visit and by study treatment.

With the aid of the MMRM analysis, 2-sided 97.5% Confidence Interval (CI) for mean change in HbA1c from baseline to 52-week visit for (10mg tirzepatide – insulin glargine) as well as for

(15mg tirzepatide – insulin glargine) will be derived. If the upper limit of the CI is  $\leq 0.3\%$ , then the respective dose of tirzepatide (10mg and/or 15mg) will be declared noninferior to insulin glargine relative to change in HbA1c from baseline.

